7.6.1 Co-Primary Safety Endpoint: Percent ECL from Preop to 6 Months Postop

7.6.2 CO-PRIMARY SAFETY ENDPOINT: UV RETINAL DAMAGE NOT DETECTABLE THROUGH ROUTINE CLINICAL EXAMINATIONS

7.6.3 Additional Safety Analyses

The following safety outcomes will be summarized descriptively based on the observed data and actual lens implanted. Results will be presented for all the RxSight LAL eyes and the Control group eyes. The 95% confidence intervals for means or percentage may be presented, as appropriate.

Adverse Events

Number and percent of study eyes will be summarized for each reported ocular AE at the operative visit and each postoperative visit for the LAL group and Control group separately. Serious ocular AEs and the non-ocular serious AEs will be summarized in the same manner. Additionally, for each of the device related AE reported during the study, the number and

percent of study eyes reported with the event will be presented. The ocular adverse events will be listed for eyes, if applicable, with IOL implantation attempted but without implantation. Ocular adverse events will be reported separately for the fellow eye.

BCDVA

BCDVA will be presented with the number and percent of eyes who fall into each category of BCDVA at each visit (e.g. 20/20 or better, 20/25 or better, 20/32 or better, etc.). The mean and standard deviation (SD) of BCDVA letter score will also be calculated for each visit. Change in BCDVA from Postop Week 3 or from Preoperative will be presented at each visit as categorical outcomes of "Increase in 15 letters or more", "Increase in 10-14 letters", "Increase in 5-9 letters", "No change", "Decrease in 5-9 letters", "Decrease in 10-14 letters", and "Decrease in 15 letters or more The mean and SD of the change from Postop Week 3 or Preoperative will also be presented. Similarly, the mean change from the prior visit to the next visit will also be summarized in the same manner.

In-Office Erythropsia Assessment (RxSight LAL only)

The number and percent of eyes in each outcome of erythropsia assessment (0- white, 1-pink, or 2- red) will be presented. In addition, the number and percent of eyes with increases in the level of erythropsia from the Postop Week 3 visit will be presented.

Daily Life Erythropsia Questionnaire (RxSight LAL only)

Results of the Daily Life Erythropsia Questionnaire will be summarized descriptively at each visit the questionnaire is completed.

City University Color Test (RxSight LAL only)

[figure not shown]
Results of the City University Color Test will be reported as the number and percent of eyes that have tritan findings >1 on Part Two of the test.

Slit Lamp Examinations

Slit lamp findings will be summarized descriptively.

Fundus Exam and Fundus Photos (RxSight LAL only)

Number of subjects with fundus exam changes from the pre-op and Postop Week 3 evaluation will be summarized.

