6.7 CLINICAL PARAMETERS

The following study parameters will be assessed as specified in Table 1 for the RxSight LAL and Table 2 for the Control IOL. Assessments will be performed using the techniques described in and in the order presented here and in Table 1.

- 1. Demographics
- 2. Daily Life Erythropsia Questionnaire (DLEQ) (RxSight LAL only)
- 3. Ocular history
- 4. History of Medications
- 5. Corneal Keratometry
- 6. Specular Microscopy (substudy)
- 7. Uncorrected distance visual acuity (UCDVA)
- 8. Manifest Refraction
- 9. Best corrected distance visual acuity (BCDVA)
- 10. In-office Erythropsia Assessment (RxSight LAL only)
- 11. City University Color Test (RxSight LAL only)
- 12
- 13. Intraocular pressure
- 14. Slit Lamp Examination
- 15. Fundus Exam
- 16. Fundus Photos
- 18. Dilated pupil diameter
- 20. Adverse Events

Table 1. RxSight LAL Schedule of Visits and Clinical Parameters

Table 1. RxSight LAL Schedule of Visits and Clinical Parameters													
Visits	Preop	Орегайче	Postop Day 1	Postop Week 1	Postop Week 3	Adjustment #2 (If needed)	Adjustment #3 (if needed)	Lock-in #1	Lock-in#2 (if nædeil)	Postop Months 1-2	Postop Mouth 6	Postop Month 12 (if needed)	Unscheduled Visit
Demographics	Х												
Daily Life Brythropsia Questionnaire (DLEQ)					х	X	х	х	х	X ⁴	х	Х	X
Ocular History	х												
History of Medications	Х	Х	X	Х	х	X.	х	Х	х	X	х	X	Х
Corneal Keratometry	х												
Specular Microscopy ³	Х				х						x		
Uncorrected distance visual actity (UCDVA)	х		х	х	М	х	Х	х	х	X	М	х	х
Manifest Refraction	х			х	M	X	х	х	х	х	M	Х	
Best corrected Visual Acuity Distance (BCDVA)	:x			X.	M	· x ·	X	х	х	х	М	х	
In-office Erythropsia Assessment					X.	Х	x	x	x	X	x	X	х
City University Color Test					Х	X	X	х	Х	Х	х	х	X ⁵
					х	X1	X1	χ¹	$\mathbf{X_{l}}$	Χı	Xi	X ¹	
Intraocular Pressure	X		х	х	х	х	х	X	х	х	X	Х	
Slit Lamp Exam	X		X	х	X	х	х	х	Х	X.	х	x	х
Fuidus Exam	X				Х	х	х	Х	X		x	х	
Fundus Photos	х				Х	х	Х	х	х		X	Х	
					х	×	х	х	x	x	x	x	
Dilated Pupil Diameter	x				х	х	х	x	х				
						χı	X ¹	Xi	X	Xi	$\mathbf{X}_{\hat{\mathbf{I}}}$	χi	
Adverse Events		х	Х	х	х	х	x	х	х	X	X	X	Х

are only required if the events described in Section 6.4.2.2 of the protocol occur.

"Tests indicated with an "X" must be performed at each unscheduled visit. Other tests may be conducted based on the investigator's assessment of the subject.

Specular microscopy will be performed on a subgroup of approximately 300 eyes including a minimum of 192 LAL eyes and 96 Control eyes.

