- Chronic anterior uveitis-anterior segment inflammation characterized by grade 1+ cell or greater (using the Standardization of Uveitis Nomenclature criteria) that is persistent for greater than 3 months postoperatively, or relapses in less than 3 months after discontinuation of therapy, or the subject is maintained on therapy for more than 3 months to control inflammation
- Corneal edema (corneal swelling (stromal or epithelial) (if present after Postop Week 1 and greater than grade 1 (trace)), OR resulting in BCDVA of 20/40 or worse at Postop Month 1-2 or later, OR (if present at Postop Month 6 of any grade)
- Raised intraocular pressure (IOP) >10 mmHg above preoperative and greater than 25 mmHg (if present after Postop Week 1) AND unrelated to mechanical pupillary block

In addition, the specific following events should be reported as an AE:

- An increase in score of more than 1 on Part 2 of the Tritan evaluation (City University Color Test) when compared to the Postop Week 3 score.
- An erythropsia score of 2 (red) at any time after Postop Week 3.
- An eythropsia score of 1 (pink) or (2) red at the Postop Month 6 visit.

All adverse events should be reported and information provided regarding whether the adverse event meets the above definitions.

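### Three score-defined AEs are reportable in either arm but only LAL eyes are tested for them, so the by-arm AE table will print 0% for Control where the accurate entry is 'not assessed'

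*Combined protocol and SAP*

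**What the plan says.** Section 8.1 closes with a short list introduced by "In addition, the specific following events should be reported as an AE". Its three items are:

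- on the color test, "An increase in score of more than 1 on Part 2 of the Tritan evaluation", with the result at Week 3 as comparator;
- on the in-office assessment, "An erythropsia score of 2 (red) at any time after Postop Week 3";
- on that same assessment, "An eythropsia score of 1 (pink) or (2) red at the Postop Month 6 visit".

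None of the three names an arm.

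Section 6.7 lists the two tests that generate these scores as "In-office Erythropsia Assessment (RxSight LAL only") and "City University Color Test (RxSight LAL only"). The Daily Life Erythropsia Questionnaire carries the same restriction. Table 1 schedules all three for LAL eyes from Postop Week 3 onward. Table 2, the Control schedule, has no row for any of them.

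The Adverse Events paragraph of Section 7.6.3 plans: "Number and percent of study eyes will be summarized for each reported ocular AE at the operative visit and each postoperative visit for the LAL" eyes, with the same display for Control. The introduction to 7.6.3 shows results for both groups and permits 95% confidence intervals for percentages. Further down, the separate summaries of in-office erythropsia, the questionnaire and the color test are headed as LAL only. The Adverse Events paragraph has no such limit.

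**The concern.** An AE that is defined by a test score can be recorded only in an eye that has the test. When the term then appears in a two-column table with all study eyes as the denominator, the untested arm shows an observed zero where it has no data. A reader of the table sees 0% for Control beside some percentage for LAL, possibly with a narrow interval, and may take it as evidence that these findings do not occur after ordinary cataract surgery. The trial does not measure that.

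Section 7.6.3 is also inconsistent with itself. It restricts the erythropsia and color-test summaries to LAL eyes, yet the same scores re-enter through the AE form into a table shown for both arms.

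**Working it through.** The plan states no figure on this point to reproduce, so the check compares the sections and then sizes the printed entry.

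**Step 1. Can a Control eye generate the event?**

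| Score-defined AE (8.1) | Can first arise | Scheduled tests, LAL (Table 1) | Scheduled tests, Control (Table 2) |
|---|---|---|---|
| Tritan increase of more than 1 | after Week 3, since Week 3 is the baseline | every scheduled visit after Week 3 | 0 |
| Erythropsia score 2 | after Week 3 | every scheduled visit after Week 3 | 0 |
| Erythropsia score 1 or 2 | Month 6 | Month 6 | 0 |

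Control eyes also have no Week 3 tritan score, so the first item is not even defined for them.

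**Step 2. Which Control cells are affected?** None of the items can arise at Week 3, and Control has no adjustment or lock-in visits (Section 6.6). That leaves Months 1-2 (first two items), Month 6 (all three) and any unscheduled visits. Restricting the table to visits common to both arms does not remove the problem, because Control is not tested at those visits either.

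**Step 3. What would be printed?** Section 6 gives 500 subjects randomized 2:1, so 500 × 2/3 ≈ 333 LAL and 500 × 1/3 ≈ 167 Control eyes, taking full attendance. With 0 events in n eyes, the exact two-sided 95% upper limit solves (1 − p)^n = 0.025:

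p = 1 − 0.025^(1/167) = 0.0218.

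The entry would be 0/167 = 0%, with a 95% CI of 0% to 2.2% if an interval is shown. The number of Control eyes scheduled for testing is 0, so the real information is 0 of 0.

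**Step 4. How many LAL events might sit opposite that zero?** The documents give no rate, so this is an illustration. After Week 3, an LAL eye has between 3 scheduled tests (lock-in 1, Months 1-2, Month 6) and 6 (two further adjustments, two lock-ins, Months 1-2, Month 6). With an assumed per-test rate q, constant and independent across tests, the share of eyes with at least one event is 1 − (1 − q)^k:

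| Assumed q | k = 3 | k = 6 | LAL eyes of about 333 |
|---|---|---|---|
| 0% | 0% | 0% | 0 |
| 0.5% | 1.5% | 3.0% | 5 to 10 |
| 1% | 3.0% | 5.9% | 10 to 20 |
| 2% | 5.9% | 11.4% | 20 to 38 |
| 5% | 14.3% | 26.5% | 48 to 88 |

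**Step 5. If an overall count of eyes with any ocular AE were produced.** The visible text does not specify one. Let other ocular AEs occur independently in a share b of eyes, and score-defined AEs in a share x of LAL eyes. The score-defined terms then add (1 − b)x to the LAL total and nothing to Control. With b = 20% assumed and x = 2%, 5% or 10%, the addition is 0.8 × x = 1.6, 4.0 or 8.0 points, against a standard error of the difference of 3.8 to 4.0 points.

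**The case against.** The best case on the other side has several parts.

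- **Control eyes receive no LDD light.** Section 6.4.2.2 uses erythropsia and tritan change to prompt evaluation for UV-related retinal damage, so a zero in Control may well be true. This stands as far as it goes. A reader might infer from the unequal testing that the Control zeros are false, or that the whole LAL excess is spurious. The documents support neither: the second would require the Control rate to equal the LAL rate, and nothing says so. What they support is that Control was not assessed.
- **No total is planned.** Section 7.6.3 works term by term, and the additions in Step 5 rest on assumed rates. A reader might infer that the overall ocular AE burden will be biased against LAL. That holds only if a total is produced, and even then some of the addition may be real treatment effect.
- **The table is descriptive.** The between-arm safety comparisons named in Section 5.2 concern endothelial cell loss, and the same section lists AE rates as a parameter for LAL eyes. This limits the consequence, but 7.6.3 still presents both arms.
- **Control subjects can volunteer symptoms** (Section 8.2). True, and such reports belong in the by-arm table. They do not make a score-defined AE possible without the test.
- **A detailed SAP is still to come** (Section 7.2). It need only be final before database lock, whereas Section 11 calls for interim reports every 6 months for the first 2 years, publicly posted, with safety summaries defined as in the final report. The table could be public before the SAP corrects it, and no visible text makes the correction.
- **Removing these AEs from the harm display could hide UV-damage signals**, which are what the study is asked to find. This is right, and the fix must keep them visible for LAL.

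**Conclusion.** The point holds as a defect of display. For three score-defined terms, the plan as written prints 0 of about 167 for Control (0% to 2.2% if an interval is given) when no Control eye was scheduled for the test. That result needs no assumed event rate; it rests only on the 2:1 split of 500, full attendance, and the tables being built as 7.6.3 describes. The true Control rate is unknown, so the LAL-Control contrast for these terms is uninterpretable.

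The reach is limited to Months 1-2, Month 6 and unscheduled visits in one descriptive safety table. No co-primary endpoint, hypothesis test or sample size is affected. The change is worth making because it is cheap and because the plan already applies the LAL-only principle a few lines further down in the same section.

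**What to change.** In Section 8.1, add '(RxSight LAL only)' to the three items.

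In Section 7.6.3, Adverse Events, state that:

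1. AEs defined by the in-office erythropsia assessment or the City University Color Test are tabulated in an LAL-only panel, with LAL eyes tested at that visit as the denominator. Control is marked 'not assessed', with no percentage and no confidence interval.
2. These AEs remain in the LAL device-related AE listing.
3. If any between-arm AE total is produced, it is shown with and without these terms.
4. Spontaneously reported color-vision complaints, which either arm can contribute, stay in the by-arm table. An LAL complaint that also has a score-defined AE is cross-referenced, so that one event is not counted twice.

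The wording should be in place before the next interim report as well as in the final SAP. The cost is a few lines of text, one extra panel and a flag on AE records that arise from the two tests. No new data, visits or subjects are needed.

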5.2 SAFETY PARAMETERS

The primary safety endpoints are:

- Median rate of endothelial cell density loss at postop month 6 compared to preoperatively compared between the LAL and Control group
- Percent of LAL eyes with UV retinal damage at postop month 6

Other Key Safety parameters

- Rates of erythropsia at each visit beginning at Postop Week 3, as evaluated by the inoffice erythropsia assessment, in RxSight LAL eyes
- Rates of erythropsia at each visit beginning at Postop Week 3, as evaluated by the Daily Life Erythropsia Questionnaire (DLEQ), in RxSight LAL eyes
- Rates of tritan anomaly on the City University Color Test at each visit beginning at Postop Week 3, in RxSight LAL eyes
- Rates of all types of adverse events, including loss of best corrected distance visual acuity (BCDVA) of ≥2 lines from Postop Week 3 visit, in RxSight LAL eyes
- In specular microscopy sub-study compared between the RxSight LAL and Control group:
 - Rate of within-eye loss of ≥25% ECD from preoperative visit at Postop Week 3 and Postop Month 6
 - Rate of within-eye loss of ≥30% ECD from preoperative visit at Postop Week 3 and Postop Month 6

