6.4.2.1 Postponement of Light Treatment Procedure(s)

LDD treatment should be delayed if any of the following new symptoms or changes in performance are noted;

- Color Vision Testing: Treatment should be delayed if the subject scores worse on Part 2 of the City University Color Test than the Pre-adjustment test for Tritan evaluation.
- Erythropsia Evaluation: With any score of 2 (red), the treatment should be delayed.
- Best Corrected Distance Visual Acuity: With any loss of BCDVA (unless the cause is known to be non-retinal) of 10 letters or more on an ETDRS (logMAR) chart compared to the Postop Week 3 BCDVA, treatment should be delayed.

- 6.4.2.2 Requirements for Additional Testing

Additional testing should be performed as soon as possible to evaluate whether UV-related retinal damage has occurred if any of the following is observed. will be performed in eyes that meet any of the following criteria:

- Significant erythropsia during in office erythropsia assessment (score of 2 (red))
- Significant erythropsia as indicated on responses to the Daily Life Erythropsia Ouestionnaire including:
 - o "severe" or "very severe" erythropsia on question 3, OR
 - o a response of "very bothersome" erythropsia on question 6, OR
 - o a response of "more than 7 days" on question 2
- Significant crythropsia as interpreted by the investigator based on spontaneous reports by the subject
- If the subject reports any level of erythropsia at the Postop Month 1-2 visit OR at any interim visit after the Postop Month 1-2 visit and <90 days after surgery based on results of the in office erythropsia assessment, the Daily Life Erythropsia Questionnaire or spontaneous verbal reports by the subject, the subject will be mailed a paper version of the Daily Life Erythropsia Questionnaire to self administer and return to the investigational site between 90-120 days after surgery. If responses to the Daily Life

² Azar D, Stark W, Dodick J, et al. Prospective, randomized vector analysis of astigmatism after three-, one-, and no-suture phacoemulsification. J Cataract Refract Surg 1997; 23:1164-1173.

Erythropsia Questionnaire indicate that there is erythropsia on question 1, the subject should have an unscheduled visit and testing should be performed.

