6.6 EXAMINATION SCHEDULE

Subjects who agree to participate in the study will return for the listed follow-up examinations for each study eye:

Evaluation	RxSight LAL	- Control
Preoperative	Day -60 to Day -1	Day -60 to Day -1
Operative	Day 0, day of surgery	Day 0, day of surgery
Postop Day 1	Days 1 to 2 postop	Days 1 to 2 postop
Postop Week 1	Days 7 to 14 postop	Days 7 to 14 postop
Postop Week 3	Days 17 to 24 postop: Adjustment #1	Days 17 to 24 postop
Adjustment #2, if needed	3 to 7 days post Adjustment #1	
Adjustment #3, if needed	3 to 7 days post Adjustment #2	
Lock-in #1	3 to 7 days post final adjustment	
Lock-in #2, if needed	3 to 7 days post lock- in #1	
Postop Months 1-2	7 to 14 days post final lock-in visit	Days 30 to 60 postop
Postop Month 6	Days 120 to 180 postop	Days 120 to 180 postop
Postop Month 12, if needed	Days 330 to 420 postop	And the state of t

A Postop Month 12 visit will be conducted if a subject is diagnosed with UV retinal damage to confirm resolution or document sequelae, if any.

Unscheduled visits falling outside the designated ranges for scheduled visits will be considered "interim" visits for data recording purposes and a report form will be completed.

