If the subject reports any degree of crythropsia at the Postop Month 1-2 visit OR at any interim visit after the Postop Month 1-2 visit and <90 days after surgery, the subject will be contacted between 90-120 days after surgery and asked to complete the Daily Life Erythropsia Questionnaire.

M Measurements will be conducted by a masked observer who will not be aware of which lens has been implanted in the eye. The masked observer should not

have access to the subject's medical and/or study records.

⁵Must be performed at any unscheduled visit which occurs at 3-months or later.

Table 2. Control IOL Schedule of Visits and Clinical Parameters

1 abie 2. Control i	IOL Schedule of Visits and C				unican i	Parameters			
Visits	dosaa	Орегайче	Postop Day I	Postop Week 1	Postop Weck 3	Postop Months 1-2	Postop Month 6	Unscheduled Visit	
Demographics	х								
Ocular History	х								
History of Medications	x	X	Х	X	X	х	Х	х	
Corneal Keratometry	x								
Specular Microscopy (substudy) ²	х				X		Х		
Uncorrected distance visual acuity (UCDVA)	х		X.	X	М	x	М	-x-	
Manifest Refraction	Х			х	M	x	М		
Best corrected Visual Acuity Distance (BCDVA)	х			x	М	х	M		
Intraocular pressure	X		Х	Х	Х	X	х		
Slit Lamp Exam	Х		X	х	Х	х	Х	х	
Fundus Exam	х				Х		х		
Fundus Photos	х				X		x		
Dilated Pupil Diameter	x				х				
Adverse Events		х	Х	X	Х	Х	х	x	

Tests indicated with an "X" must be performed at each unscheduled visit. Other tests may be conducted based on the investigator's assessment of the subject. Specular microscopy will be performed on a subgroup of approximately 300 eyes including a minimum of 192 LAL eyes and 96 Control eyes, Measurements will be conducted by a masked observer who will not be aware of which lens has been implanted in the eye. The masked observer should not have access to the subject's medical and/or study records.

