7.6 SAFETY PARAMETERS

[figure not shown]
All data analyses will be based on the observed data and actual lens implanted. No imputation will be performed for the missing data.

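### Does the DLEQ erythropsia rate need a written case definition and denominator for the time points that reach only some LAL eyes?

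*Combined protocol and SAP*

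**What the plan says.** Section 5.2 (repeated in the synopsis) carries this item in its list of further key measures: "Rates of erythropsia at each visit beginning at Postop Week 3, as evaluated by the Daily Life Erythropsia Questionnaire (DLEQ), in RxSight LAL eyes". The only analysis text for it is in Section 7.6.3: "Results of the Daily Life Erythropsia Questionnaire will be summarized descriptively at each visit the questionnaire is completed". Section 7.6 bases all safety analyses on observed data: "No imputation will be performed for the missing data".

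Table 1 in Section 6.7 marks the DLEQ at every LAL visit from Postop Week 3 on, including the visits held only if needed, and at unscheduled visits. A further administration falls between visits. Under Section 6.4.2.2, a subject who reports any erythropsia at Months 1-2, or at a later interim visit before day 90, is followed up between days 90 and 120: "the subject will be mailed a paper version of the Daily Life Erythropsia Questionnaire to self administer and return to the investigational site". The Table 1 footnote words it as "the subject will be contacted between 90-120 days after surgery and asked to complete the Daily Life Erythropsia Questionnaire". If question 1 on that form is positive, "the subject should have an unscheduled visit and testing should be performed". Section 6.6 restricts the last visit: "A Postop Month 12 visit will be conducted if a subject is diagnosed with UV retinal damage".

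Section 6.4.2.2 also holds two DLEQ criteria, both used to trigger action. One is any erythropsia on question 1. The other is a composite for significant erythropsia built from questions 2, 3 and 6. Section 7.2 promises a detailed statistical analysis plan before database lock.

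**The concern.** A rate needs a numerator and a denominator, and Section 7.6.3 writes down neither for the DLEQ. Its neighbours in the same section are more specific. The in-office test has three outcome levels, and "the number and percent of eyes with increases in the level of erythropsia from the Postop Week 3 visit will be presented"; the color test has a cut-off for tritan findings.

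The denominator matters most at days 90-120. Everyone asked then has already reported erythropsia, so a percentage of completed forms describes persistence among earlier cases and not frequency in LAL eyes. If it were shown in a row of per-visit rates, a reader would take persistent erythropsia to be several times more common than it is. If the mailed form were left out because it is not a visit, a reading between Months 1-2 and Month 6 would disappear from the tables. The protocol treats any erythropsia from three months on as a reason to test for UV retinal damage, which is one of the two post-approval questions, so neither outcome would be welcome.

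**Working it through.** The documents state no DLEQ rate, sample size or precision, so there is no figure to reproduce. The check has three parts: who is asked at each time point, how large the distortion could be, and whether the plan's text leads to it.

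**1. Who is asked** (Section 6.4.2.2, Section 6.6, Table 1)

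| Time point | LAL eyes asked |
|---|---|
| Week 3, Lock-in #1, Months 1-2, Month 6 | All |
| Adjustments #2 and #3, Lock-in #2 | Eyes that need that treatment |
| Days 90-120 (mailed) | Subjects with erythropsia at Months 1-2, or at a later interim visit before day 90 |
| Unscheduled visits | Every eye seen, whatever the reason |
| Month 12 | Eyes diagnosed with UV retinal damage |

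Only the mailed form is selected directly on erythropsia. Unscheduled visits are defined by timing, with the DLEQ mandatory at all of them. A positive mailed form is one route to such a visit, so that group is mixed and self-selected. Month 12 follows a retinal diagnosis, and the testing that leads there can also be prompted by a tritan change or an unexplained loss of best corrected acuity.

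**2. Possible size at days 90-120**

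LAL eyes: 500 × 2/3 ≈ 333 (Section 6). With m eyes mailed and all forms returned, the percentage of mailed eyes divided by the percentage of all LAL eyes is 333/m, whatever the number positive. The share mailed is an assumption.

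- 5% mailed: m = 17, ratio 333/17 = 19.6
- 10% mailed: m = 33, ratio 333/33 = 10.1
- 20% mailed: m = 67, ratio 333/67 = 5.0

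Example with m = 33 and 8 positive (both assumed; exact 95% intervals): 8/33 = 24.2% (11.1 to 42.3) of mailed eyes, and 8/333 = 2.4% (1.0 to 4.7) of LAL eyes. If only 26 forms come back, 8/26 = 30.8% of those returned. The 7 unreturned forms allow from 8/333 = 2.4% to (8 + 7)/333 = 4.5% of LAL eyes, counting only the eyes that were mailed a form.

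The ratio is therefore large for any small mailed group. It becomes an error only if the percentage of completed forms is labelled as the rate in LAL eyes.

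**3. Does the text lead there?**

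Section 7.6.3 summarizes the DLEQ by visit. The mailed form is not a visit in Section 6.6 and has no column in Table 1. No sentence proposes its percentage as a rate in LAL eyes.

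If the form is left out of the per-visit tables, little is lost on the positive side. A positive question 1 calls for an unscheduled visit, where the DLEQ is mandatory, and any erythropsia there at three months or later calls for additional testing. Every LAL eye is asked again at Month 6. Without postponed treatments, the LAL Months 1-2 visit falls between day 17 + 3 + 7 = 27 and day 24 + 4 × 7 + 14 = 66. Month 6 runs from day 120 to 180. The gap is thus 120 − 66 = 54 to 180 − 27 = 153 days, and the mailed form with its follow-up visit sits inside it.

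**4. Case definition**

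Section 5.2 asks for rates of erythropsia without qualification. In Section 6.4.2.2, question 1 is the item that shows whether erythropsia is present. Section 7.2 summarizes categorical variables by frequencies and percentages, so question 1 would be tabulated at each visit in any case.

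The composite cannot be rebuilt from item frequencies, because its items overlap to an unknown degree. If each of the three met its threshold in 3% of eyes (assumed), the composite could lie anywhere from 3% (complete overlap; 0.03 × 333 ≈ 10 eyes) to 9% (no overlap; 0.09 × 333 ≈ 30 eyes). But no section promises a composite rate; it serves as a trigger for testing.

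**The case for a change.** The strongest case for a change is about timing. The detailed analysis plan is due only before database lock, while Section 11 requires interim reports every six months for the first two years. Those analyses are made public, and their safety summaries are defined as in the final report. The DLEQ definition is therefore needed well before lock. Phase A was run to build this questionnaire, the remedy would use criteria and data already in the protocol, and it would cost one paragraph and a table shell.

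Several parts of this stand. Section 7.6.3 is less specific about the DLEQ than about the tests beside it. The mailed group is selected on earlier erythropsia, and the text does not say where its results go. An analyst preparing an interim report will have to choose a convention.

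It falls short because the choice is not a hard one. Presence on question 1, among eyes asked at each visit and with the number asked shown, follows from Sections 5.2, 6.4.2.2 and 7.2 together. A competent table for the mailed form gives the numbers mailed, returned and positive. The several-fold overstatement needs an assumed mailed share and also a presentation that the plan does not describe. Change from Week 3 and a composite rate would be additions of preference; their absence breaks no promise.

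**Conclusion.** No change to the plan follows. This is missing detail that analysts fill sensibly. At the four time points where the questionnaire is due in every LAL eye, the rate in Section 5.2 is obtained as written, apart from ordinary missing forms. The remaining time points are conditional by design, and showing the number of eyes asked makes that plain.

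The 5- to 20-fold ratio is arithmetic on assumed mailed shares of 20% down to 5%. It describes a misreading that the plan does not commit to. The result is descriptive, secondary and confined to one arm, and no primary endpoint or test depends on it.

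The conclusion rests on taking question 1 as the item for presence, as Section 6.4.2.2 uses it, and on the detailed analysis plan setting the table layout. Neither that plan nor the questionnaire is in the public text, so a scoring rule may already exist.
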